Once enrolled, the participants will be randomly assigned to control or treatment group. The control group participants will receive the gold standard treatment for V shaped lesions - a resin modified glass ionomer (Photac-fil®). Treatment group participants will receive their V shaped lesion restoration with Biodentine™. When they receive the restoration, all treatments will follow the standard of care for their placement and polishing at the UMSoD. Participants will be assigned a random number to identify them and will be blinded as to which treatment they will receive. Participants will fill out the same OHIP-49 and BPI questionnaire via a

survey link at 1 week, 2 weeks, and 3 months post treatment. If participants complete the survey, they will receive a monetary compensation of \$10 dollars/group of surveys completed for a potential of \$40 dollars to ensure participant compliance with the survey. Surveys will be completed at recall appointments on a secure survey system maintained by the UM medical school, REDCap and data will be stored on REDCap and backed-up to a secured University of Michigan Server. Expert assessors collecting patient information will be blinded as to the treatment the participant receives. At 3 months, the patients will receive a follow up evaluation of the filling, and an evaluation of the restoration placed at the V shaped lesion. Table 1 gives a visual breakdown of the study design. The restorative materials used in this study will be placed following manufacturer's instructions.

Table 2: Study Design

Timeline	Control Group (group size: 20) Study enrollment assigned random number	Treatment Group (group size: 20) Study enrollment assigned random number
Prescreen	Oral exam, dental prophylaxis, (Part of standard of care at UMSoD) pre-screen questionnaires modified from BPI	Oral exam, dental prophylaxis, (Part of standard of care at UMSoD) pre-screen questionnaire modified from BPI
Day 1 – Baseline	OHIP-49 BPI questionnaire	OHIP-49 BPI questionnaire
Day 1 - Baseline	Treatment: PHOTACFIL®	Treatment: BIODENTINE™
Week 1 - Follow-up (survey will be emailed and should be completed within 7 days)	OHIP-49 BPI questionnaire PGIC Scale	OHIP-49 BPI questionnaire PGIC Scale
Week 2 - Follow-up (survey will be emailed and should be completed within 7 days)	OHIP-49 BPI questionnaire PGIC Scale	OHIP-49 BPI questionnaire PGIC Scale

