Prior to testing primary study aims, we will examine data distribution characteristics to identify outliers and determine suitability of the data for parametric testing. Bivariate correlations will be conducted to identify important covariates for inclusion in main statistical models (e.g. age). Assuming underlying assumptions are met, we will use repeated measures of general linear models (GLM) to test for significant differences between the control and treatment groups in terms of changes in pain (specific aim 1) and oral health related quality of life (specific aim 2) over the course of the study. Significant group versus time effects will be examined graphically to determine the nature of the interaction and to qualify how pain and oral health related quality of life changed over time for each group.

Power Analyses

Currently, we do not have input data available to do an adequate sample size analysis or the study. For this small pilot study, we planned for a sample of 40 participants (20 subjects in control group and 20 in the experimental group) to generate some preliminary data for conducting a rigorous sample size analysis for a larger clinical trial

Potential Problems and Alternatives Strategies

In the event that we do not recruit enough patients to fulfill project timeline, we can recruit patients from the graduate clinic at the University of Michigan School of Dentistry and the emergency clinics.

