In the event that either the control or treatment restoration falls off we will offer to replace the restoration and we will continue the measurement procedures. Due to the locations of the class V lesions, the stresses of the restoration during mastication may promote debonding of the restorations however, Biodentine has an increased risk of debonding. According to the manufacturer, Biodentine bonds well with dentin; however, no studies exist evaluating its bond strength in class V cervical lesions. If the Biodentine debonds, we will place a base layer of Biodentine to cover and seal the dentin and place Photac-fil® over top of that for added retention. This will allow Biodentine to remain in contact with the dentin but be more retentive. If a Biodentine restoration is placed in a shallow lesion that does not have a lot of natural retention, we will automatically place a Biodentine layer that is covered by Photac-fil®. Loss of restorative material will be covered under the grant for up to six months after initial placement of the restoration and will be noted in the patients record. If a participant has a restoration replaced, a new time line will be started for post-treatment evaluations just like a newly placed restoration. Additionally, Biodentine™ is not offered in multiple shades and patients may request that it is covered with a more esthetic restoration after the study is completed at the University of Michigan School of Dentistry (UMSoD).

Project feasibility

The undergraduate clinics have over 5,000 male and female patient visits per month for treatment of patients aged between 18-60. New patients are screened daily at the school and are continuously added to the patient population at the UMSoD. We plan to recruit from the dental undergraduate clinic. While we do not foresee enrollment issues, we can also access over 3,000 more patients in other clinics at the UMSoD by including the graduate clinics and faculty clinic. Given the high numbers of patients seen at the school of dentistry, we do not anticipate any difficulties in recruiting patients to meet enrollment numbers for the study.

Project Management and Project Timeline

The project principal investigator is [name] [name] and co-investigator is [name]. We will train and calibrate dental students to apply the materials as well as collect participant assessments as

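### A replaced restoration restarts the follow-up schedule, but the SAP does not say which scores are analysed; using restarted scores can remove failure-related pain unequally by arm

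*Combined protocol and SAP*

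**What the plan says.** Under Potential Problems and Alternatives Strategies, the protocol says that if a restoration in either arm is lost, "we will offer to replace the restoration and we will continue the measurement procedures". The same paragraph then adds: "If a participant has a restoration replaced, a new time line will be started for post-treatment evaluations just like a newly placed restoration". It does not say whether original visits still due are kept, or whether restarted scores replace those already collected.

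The paragraph expects unequal loss ("Biodentine has an increased risk of debonding") and gives no rate. Replacement is "covered under the grant for up to six months after initial placement of the restoration and will be noted in the patients record". In the Biodentine arm, a debonded restoration is replaced by a Biodentine base covered with Photac-fil, the control material.

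The Statistical Analysis Plan states: "we will use repeated measures of general linear models (GLM) to test for significant differences between the control and treatment groups". The outcomes are change in pain (aim 1) and in oral health related quality of life (aim 2). It has no rule for participants whose restoration was replaced. Power Analyses describes a pilot of 20 per arm, intended "to generate some preliminary data for conducting a rigorous sample size analysis for a larger clinical trial".

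**The concern.** The restart is triggered by an event after randomisation that the protocol expects more often in one arm. Specific Aims attributes the pain to exposed dentin, and Table 2 expects placement to eliminate pain at once. A tooth that has lost its restoration should therefore hurt more than a restored one.

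If a restarted survey takes the place of an original one, a score recorded while the tooth was bare gives way to a score from a fresh restoration. Where that happens more often with Biodentine, the comparison moves in its favour. In that arm the restarted scores also describe a different restoration, since the replacement is covered with the control material.

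Two analysts following the text could build different datasets from the same participants. The effect estimate passed on to the larger trial would then depend on an unstated choice.

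**Working it through.** The plan has no figure to reproduce here: it gives no loss rate, repair delay, pain gap or SD.

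**Inputs from the documents.** 20 per arm; visits at 1 week, 2 weeks and 3 months, the last with a window of three weeks either side (Table 2); replacement covered for six months. The only pain rating among the listed pre-screen questions asks about the worst pain of the past week (Study procedures), so recall is taken as 7 days.

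**Assumed inputs.** Loss by day 91 of 20% (Biodentine) and 5% (control); pain 5 points higher while lost than when restored; repair 14 days after loss; each loss replaced once. Participants enter with pain above 6 on a 1-10 scale and Table 2 expects its elimination, so a gap of 4 to 6 is plausible, but it is not stated.

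**Formula.** Shift towards Biodentine at visit day t = (pB − pC) × gap × F. F is the share of 91-day losses falling between t − delay − recall and t. Restarted visits come at least 7 days after replacement, so with one-week recall they do not reach back to the loss.

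**Middle case.** (0.20 − 0.05) × 5 = 0.75.

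| Visit | Losses even over 91 days | Half of losses in days 0-14, rest even |
|---|---|---|
| Week 1 | 0.75 × 7/91 = 0.06 | 0.75 × 0.25 = 0.19 |
| Week 2 | 0.75 × 14/91 = 0.12 | 0.75 × 0.50 = 0.38 |
| Month 3 | 0.75 × 21/91 = 0.17 | 0.75 × 0.5 × 21/77 = 0.10 |

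**Month-3 range**, with Biodentine loss 10-30%, gap 4-6, delay 7-28 days and either timing:
- Low: (0.10 − 0.05) × 4 × 0.5 × 14/77 = 0.02.
- High: (0.30 − 0.05) × 6 × 35/91 = 0.58.

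**Check with another loss model.** With a constant hazard over 90 days, 30% versus 10% loss, a 4-point gap and the same 21-day window, the shares affected are 1 − 0.70^(21/90) = 0.080 and 1 − 0.90^(21/90) = 0.024. The shift is 0.056 × 4 = 0.22, the same order.

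**Scale.** The 95% half-width for a difference in means is 2.024 × SD × √(2/20), which is 1.28 at SD 2 and 1.92 at SD 3 (assumed).

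**What the visit window does.** Take a loss on day 80 repaired on day 94. Restarted visits fall on days 101, 108 and 185, and none recalls the loss. The original month-3 survey captures the pain only if completed on about days 80 to 101, while its window runs from day 70 to day 112 (91 ± 21). That is roughly half the window. The figures above fix month 3 at day 91.

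**When month 3 does not move.** A loss repaired well before month 3 leaves both the original and the restarted month-3 scores free of it. A loss after the original month-3 survey does not shift that result in this model either. It does produce a second full set of surveys, ending as late as day 182 + 91 = 273, and the SAP does not say which set counts.

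**The case against.** The strongest reply is that the two sentences are compatible: measurement continues, on the new clock. On that reading the protocol does say which schedule applies after replacement. This stands in part. The clear gap is narrower: which scores count when original visits were already completed. A score recorded while the tooth was bare usually belongs to that group, because it was collected before the repair.

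A second reply is that every rate here is assumed and that the study is a 40-person pilot with no power claim. That is correct and sets the severity. It does not remove the omission, since the SAP still plans a significance test.

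Mitigating facts also stand. Replacement is only offered. In shallow lesions, "we will automatically place a Biodentine layer that is covered by" Photac-fil from the start. If half the Biodentine restorations were covered and then lost at the control rate, loss would be 0.5 × 0.20 + 0.5 × 0.05 = 0.125, the difference would fall from 0.15 to 0.075, and the middle-case shifts would halve. If only 80% of losses were replaced, they would be multiplied by 0.8.

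Three stronger readings are tempting, and the documents do not support them:
- **Biodentine failures are hidden.** Loss is noted in the patient record, and "At 3 months, the patients will receive a follow up evaluation of the filling". The information is kept; no planned analysis uses it.
- **More frequent Biodentine loss alone biases month 3.** The loss must also be unrepaired at that visit or within its recall period, and pain must return.
- **The direction reverses at weeks 1 and 2 under one-month recall.** The pre-screen introduction mentions a month, but the only rating question listed covers one week. A 30-day item at those visits would also reach pre-treatment pain in every participant.

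**Conclusion.** The concern holds as a minor one. The restart rule is explicit, the SAP has no rule on which scores enter the model, and one permissible choice removes failure-related pain more often from the arm expected to fail more.

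The month-3 shift is about 0.17 points (even losses) or 0.10 (early losses) in the middle case, and 0.02 to 0.58 over the range examined. It is zero if the shares lost and unrepaired at, or within recall of, the visit are equal between arms, if pain does not return on loss, or if original-schedule scores are analysed. All of these figures lie below the sampling uncertainty of 1.3 to 1.9 points. Unlike sampling error, though, the shift has a direction and would carry into the planning of the larger trial.

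A reader might infer that the trial will be biased towards Biodentine. The documents do not support that, because they do not say that restarted scores will be used. No figure can be given for OHIP-49 (aim 2), since neither its score range nor its recall period is stated.

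**What to change.** Add to the SAP:
- All outcomes are analysed by randomised group at 1 week, 2 weeks and 3 months after first placement, whether or not a restoration was replaced.
- Original-schedule surveys still due continue after a replacement.
- Restarted surveys do not overwrite original scores and are used only in a labelled sensitivity analysis, where they still answer a question about restorations that stay in place.
- An original survey already superseded by a restart is treated as missing, and the number is reported by arm. This may already apply: the document is dated July 2018, and Table 3 ends enrolment in the preceding quarter.

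State the recall period of each analysed pain item. Clarify that "we will offer to replace the restoration and we will continue the measurement procedures" includes the original schedule. Record the dates of loss and replacement, and report both by arm with exact 95% confidence intervals. These will be wide: 1/20 gives 0.1-24.9% and 4/20 gives 5.7-43.7%. No change to clinical handling is proposed.

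**Cost.** A few SAP sentences, two date fields, and some overlapping surveys and reminders for replaced participants. In the middle case (4 + 1 replaced, 14-day delay) the only original visit still due is month 3. That is 77/91 = 0.85 sets each with even losses, or 0.5 + 0.5 × 63/77 = 0.91 with early losses, about $42 to $45 in total at $10 per set if paid. With 7 replaced participants and three sets each, the ceiling is $210. The result may look slightly less favourable to Biodentine.

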1.2. Sources of Materials

1.3. Data collection methods. The data obtained will be used specifically for research purposes, including: a modified Brief Pain Inventory (BPI) to reflect oral pain, OHIP-49 questionnaire and the Patient Global Impression of Change (PGIC) Scale identified only by the enrollment number that will be given to the patients. Participants will take the BPI, OHIP-49 at their first appointment, one week later, 2 weeks after the placement of the restoration and 3 months after the placement of the restoration. The PGIC survey will be given in addition to the other surveys one week after the placement of the restoration, 2 weeks after the placement of the restoration and 3 months after the placement of the restoration. Surveys will be generated on REDCap and emailed to participants to complete the survey. Daily email reminders to complete the surveys will continue until the surveys are completed.

1.4. Potential risks. Overall, potential risks associated with the participation in the study are low risk. The proposed treatments, more specifically the dental restorations, will not involve either a tooth preparation.

1.4.1. Physical. There is little likelihood of any physical risk as a result of participation in this research project. The participants will be not exposed to any physical harm. The study will be conduct at the UMSoD clinics in appropriated dental settings.

1.4.1.1 Management. Also, given the pain the patients may experience prior to the placement of the restorative material, patients may require local anesthetic during the application and finishing of the restoration. Topical anesthetic will be first applied to the gingiva and if necessary, patients may receive a carpule of 2% lidocaine HCl containing 1:100,000 epinephrine which is the standard anesthetic used in patients at the University of Michigan School of Dentistry to manage pain. The use of the local anesthesia will be limited to two carpules, 3.6ccs. This dosage is well tolerated and within the dosing considerations for patients with some associated risks with epinephrine. This amount of local anesthesia is also considered the standard of care at UMSoD. Participants will understand the minor discomfort that can be associated with EPT testing and palpation of the salivary glands.

1.4.2. Psychological. Participants will be asked to provide information about their self-reported pain associated with tooth sensitivity and to answer the OHIP-49 questionnaire, BPI survey and PGIC survey. These questions have a small likelihood of low psychological risk. If participants demonstrate to be uncomfortable or emotionally disturbed by the questionnaires, they will be reminded that there is absolutely no obligation to fulfill the questionnaires. In these cases, the patients will still receive the dental care proposed in this study.

2. Protection Against Risks

2.1. Recruitment and informed consent. For recruitment, we will distribute flyers at the UMSoD and we will send emails to the dental students (dental providers) about information on the study. Volunteers who are

interested in an alternative treatment for tooth sensitivity will be examined per the guidelines of the UMSoD, informed about the study and take a pre-screen questionnaire. After selecting the volunteers under the inclusion and exclusion criteria, patients will receive a random number at the study enrollment session. From this point on, we will only identify the patients by the given enrollment random number and age. A well-trained team of third and fourth-year dental students will deliver the dental care including the restorations in the Foundations Clinic at the UMSoD and will be supervised by [name] and [name]. The dental care treatments proposed in this study are part of the second year dental students competency requirement. We strongly believe that the third and fourth year dental students are entirely competent to delivery such treatments based on the competencies they passed in their first and second years of their dental training. A second team of dental students that are blinded to the treatment will collect and analyze the data at the designated time points. Prior to conducting any treatment and assessing the self-perceived outcomes, all participants will be given a formal Statement of Consent Form to read. The interviewer will verbally explain the form by the following study team members: [name] or [name] and the study coordinator, [name], if necessary. Participants will sign the form indicating that they understand that they are being asked to participate in a research study, that they understand the risks involved in participating, that they can refuse to answer any question that they are not comfortable with, and that the information they provide will be kept strictly confidential. The informed consent form will also provide assurances that their participation in the research aspect of this project will in no way affect their patient status either positively or negatively.

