For very symptomatic V shaped lesions, a resin-modified glass ionomer restoration may be the preferred treatment [9, 10, 12]. This material covers and seals the dentin tubules, providing a protective layer where the cementum has worn away. However, resin-modified glass ionomer restorations do not always reduce or diminish the tooth pain because the chemical makeup of resin-modified glass ionomers themselves may trigger tooth irritation through an inflammatory response in the pulp [13]. Therefore, it is important to evaluate new dental materials that may be more effective in treating the pain associated with tooth sensitivity with fewer negative sequelae. A new biocompatible and bioactive material (Biodentine™) is available. Biodentine™ has a wide range of clinical applications because of its similarity to the dentin and its mechanisms of dentin adherence. Furthermore, Biodentine™ has been successfully used as a safe dentin substitute in clinical studies[14]. However, the effect of Biodentine™ to reduce tooth pain in V shaped lesions is unknown.

We propose to investigate the effect of Biodentine™ as a restorative dental material on V shaped lesions with a randomized single blind controlled study. Specifically, we will investigate how Biodentine™ treatment affects oral health related quality of life. Because Biodentine™ is a biocompatible and a bioactive material, which is considered a dentin substitute material, we hypothesize that Biodentine™ is a more effective way of treating tooth pain associated with V shaped lesions compared to traditional resin-modified glass ionomer restorations. To evaluate the effects of Biodentine™ as a dental restorative material, we will compare the treatment with Biodentine™ to the resin modified glass ionomer, which is a dental material widely used to restore V shaped lesions. In addition, we will evaluate the impact on oral health via patient self-reporting of pain and daily activities with an oral health related quality of life questionnaire before and after treatment at multiple time points.

Specific Aims (SA):

SA1: Investigate whether Biodentine™ is more effective compared to resin-modified glass ionomer in reducing tooth pain in V shaped lesions

SA 2: Investigate whether Biodentine™ is more effective compared to glass resin-modified ionomer in improving general oral health-related quality of life in patients with V shaped lesions.

[figure not shown]

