2.2. Protection against risks

2.2.1. Minimizing physical and psychological risks. Participants are free to refuse to respond to any question that may result in psychological disturbance. Written information collected is for research purposes only and will not become part of their personnel chart records. Individual responses to our questionnaires will not be linked to identifying information, except for age, and will not at all influence current or future delivery of dental care at the UMSoD. These precautions are expected to effectively eliminate risks associated with the study participation. Management of complications of epinephrine and systemic medications, such as propranolol, will be mitigated by allowing participants to receive a maximum of two carpules of 2% lidocaine HCl containing 1:100,000 of epinephrine which is well within the recommended dose for epinephrine and patients with cardiovascular complications.

2.2.2. Minimizing risks to confidentiality. Identifying information from any of the participants in the study will be kept separately from the forms on which they record their responses to the questions. The participants identifying information will be safely stored at the University of Michigan Mident Axium system as any other patient assisted at the UMSoD. Records will be linked to individuals only through the enrollment number and the information used to link records with identifying information will be kept in a securely file drawer in a locked room only accessible to project principal investigators. Names and any other identifying information collected will be kept in a locked file drawer in a locked room only accessible to the project principal investigators and study coordinator. References to names or other identifying information will be eliminated from the written transcript of the interview in preparation for analysis of qualitative data. Names and any other identifying information will be eliminated in preparation for analysis of these records. These are precautions that we expect to be completely effective in eliminating risks to confidentiality. Email identifiers in the surveys will also be eliminated during analysis of the study.

3. Potential Benefits

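### Section 1.4.1 rules out physical harm, against the protocol's own statements on debonding and pulp irritation, and restoration failures are not planned as study data reported by arm

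*Combined protocol and SAP*

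**What the plan says.** **The risk section.** Section 1.4.1 (Physical) opens with "There is little likelihood of any physical risk as a result of participation in this research project" and continues with "The participants will be not exposed to any physical harm". Section 1.4.1.1 then covers local anesthetic and ends with "Participants will understand the minor discomfort that can be associated with EPT testing and palpation of the salivary glands". Sections 1.4.2 and 2.2 deal with psychological risk, confidentiality and epinephrine. None of them mentions a risk arising from either restorative material.

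**The rest of the protocol.** Potential Problems and Alternatives Strategies says that "Biodentine has an increased risk of debonding", adds that bond strength in class V cervical lesions has not been studied, and sets out what happens if a restoration is lost. The Specific Aims say that "resin-modified glass ionomers themselves may trigger tooth irritation through an inflammatory response in the pulp"; the control arm receives a material of this class.

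**What is recorded and analysed.** Loss of material "will be noted in the patients record". Study Procedures schedules an evaluation of the filling at 3 months, without stated criteria. Section 1.3 lists the research data as the modified BPI, the OHIP-49 and the PGIC. The Statistical Analysis Plan covers pain and oral health related quality of life only. After a replacement, the post-treatment timeline starts again. No section defines, collects or reports adverse events.

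**The concern.** There are two linked problems.

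The first is a contradiction. A categorical statement that no physical harm will occur cannot stand beside an acknowledged, raised and unquantified risk of failure in one arm and a possible pulp reaction to the material used in the other. These are the risks attached to what is being randomised, and the risk section leaves them out.

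The second is statistical. Failure of the restoration is the clearest cost the protocol itself attaches to the new material, yet no count of failures by arm is planned. The restart rule adds to this: a participant whose restoration is lost and replaced begins a fresh series of post-treatment surveys, and the plan does not say what becomes of the surveys already completed. If only the new series is analysed, the failure leaves no trace in the results. If failures are more common with Biodentine, as the protocol suggests, the omission falls unevenly. A benefit in pain could then be reported without its failure cost, and the larger trial for which this pilot is meant to supply data would lack a failure rate to plan with.

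**Working it through.** The plan states no figure on this point, so there is nothing to reproduce. The check compares the sections and then asks what 20 per arm could show.

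**Step 1: is there a contradiction?**

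| Place | Content |
|---|---|
| 1.4.1 | Physical harm ruled out, directly after a sentence calling physical risk unlikely |
| 1.4.1.1 | Anesthetic, pulp testing, gland palpation |
| Potential Problems | Debonding risk increased for Biodentine; bond strength unstudied in these lesions |
| Specific Aims | Control class of material "may trigger tooth irritation through an inflammatory response in the pulp" |

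The last two rows name risks of the restorations; the first two name none. The statements do not agree. The debonding statement is firm as to direction. The pulp statement says only that irritation is possible.

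**Step 2: would a failure reach the results?** It is noted in the patient's record, but section 1.3 does not list it as research data. The 3-month evaluation would see a restoration missing at that time, but it has no criteria and no line in the analysis. Pain after a loss could appear in the BPI, but as an outcome score rather than as an event, and the restart may supersede that score. No route leads to a count by arm.

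**Step 3: what could 20 per arm show?** The sample size (20 + 20 = 40) is in Power Analyses. All debonding rates below are assumptions, because the documents give none.

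Chance of at least one affected participant in an arm, 1 − (1 − p)^20:
- p = 5%: 1 − 0.95^20 = 64%
- p = 10%: 1 − 0.90^20 = 88%
- p = 20%: 1 − 0.80^20 = 99%

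Two-sided exact 95% upper limit if no event is seen in 20: 1 − 0.025^(1/20) = 16.8%. The one-sided 95% limit is 1 − 0.05^(1/20) = 13.9%.

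Approximate power for a difference between arms, two-sided 5%, n = 20 per arm: Φ[(d − 1.96·SE0)/SE1]. Here d is the difference in rates, SE0 = √(p̄(1 − p̄)·2/n) with p̄ the mean of the two rates, and SE1 = √((p1(1 − p1) + p2(1 − p2))/n).
- 5% against 20%: SE0 = √(0.125 × 0.875 × 0.1) = 0.1046; SE1 = √((0.0475 + 0.16)/20) = 0.1019; (0.15 − 0.2050)/0.1019 = −0.54; power 29%
- 5% against 30%: power 55%
- 5% against 40%: power 78%

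The normal approximation is rough at these counts, but the message is clear. At such rates an event would probably occur in an arm, and the pilot could describe it. It could not reliably test a difference unless that difference were very large.

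**The case against.** The strongest reply is that the plan does not ignore failure. It anticipates loss of a restoration, provides for replacement, has the loss noted and examines the filling at 3 months. The BPI, OHIP-49 and PGIC are collected in both arms at three follow-up times, so worsening pain would register. The disputed sentence follows a softer one. Pulp irritation is stated only as a possibility, and it belongs to the material the protocol calls the gold standard. Loss of a restoration is arguably a device failure rather than physical harm, and the documents do not classify it.

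Much of this stands, and it rules out several stronger readings:

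- *That failures go unrecorded or unchecked.* They are noted and the filling is examined. What is missing is their status as study data and a place in the analysis.
- *That participants are not told of these risks.* The consent pages were removed from the text, so the point concerns the risk section only.
- *That section 2.2.1 claims restoration risks are eliminated.* The sentence "These precautions are expected to effectively eliminate risks associated with the study participation" follows precautions about refusing questions and keeping responses unlinked. It is loosely worded, but it is not about restorations.
- *That local anesthetic risk is denied.* It is addressed in 1.4.1.1 and again in 2.2.1.
- *That events are not collected because harm was assumed absent.* No section gives a reason.

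What the reply does not answer is the flat sentence itself, which cancels the softer one before it, and the absence of any count by arm alongside a restart rule that can hide failures.

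**Conclusion.** The point holds in this limited form. Section 1.4.1 conflicts with the protocol's own account of debonding and of possible pulp irritation. A restoration failure that may differ by arm has no planned route into the reported results.

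Its size cannot be expressed as a bias, because no debonding rate is given. At assumed rates of 5% to 20%, the chance of at least one affected participant in an arm is 64% to 99%, so the gap would probably matter in practice. The zero-event limit (16.8% two-sided) shows how little 20 participants can exclude; it does not measure the defect.

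The conclusion rests on two assumptions. Loss of the seal may bring back pain or require re-treatment, which is plausible on the protocol's rationale but not stated as a consequence. And surveys from before a replacement may be superseded, which the restart rule allows but does not spell out. A reader might infer that the pilot ought to compare safety between arms formally; 20 per arm does not support that.

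**What to change.** 1. Reconcile section 1.4.1 with the Specific Aims and with Potential Problems and Alternatives Strategies. Replace the categorical sentence with one naming the two material-specific risks at the strength the protocol gives them: debonding as increased for Biodentine, and pulp irritation as possible for the control.
2. Record as study data, with dates, each debonding or replacement and any new or worse problem with the treated tooth. Use the 1-week, 2-week and 3-month surveys and the 3-month check of the filling. A general problem item alone is not enough; debonding and replacement need their own dated entry because they restart follow-up.
3. Add a line to the Statistical Analysis Plan: the number of participants with each event by randomised arm, with exact two-sided 95% limits, described without a test. Count participants rather than restorations, since a participant may have two sites filled.

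The cost is an amendment, a small data-collection item and a slightly less favourable risk statement. No extra visit is needed, and the clinical handling of a lost restoration is unchanged.
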